# 6.3.1.2 Cohort A Substudy (≥65 Years): Sensitivity, Supplementary, and Subgroup Analyses

To assess the consistency of immunogenicity response of mRNA-1083, sensitivity and subgroup analyses of the co-primary endpoints will be conducted based on the PP Immunogenicity Set. A supplementary analysis may be conducted on the Immunogenicity Set if the number of participants in the PPIS and the Immunogenicity Set differs (defined as the difference divided by the total number of participants in the PPIS) by more than 10%. The same statistical methods as for primary analysis will be used for the sensitivity, supplementary and subgroup analyses.

The primary immunogenicity endpoints may be analyzed by subgroup categories available in Table 4. Adjustment will be done for the stratification factors (age and influenza vaccine status) when applicable and 95% CIs will be calculated. If the number of participants in a subgroup category is less than 10% of sample size in the analysis set, it may be combined with other categories for the subgroup analyses.

#### 6.3.1.3 Cohort B Substudy (≥50 to <65 Years): Primary Analyses

The primary objective of Cohort B is to evaluate the immunogenicity response between the participants receiving mRNA-1083 (40  $\mu$ g) + Placebo and those receiving Fluarix + Spikevax among the adults 50 to <65 years of age. Immune responses for influenza, as measured by GM level and SCR at Day 29 by HAI assay in the group of mRNA-1083 (40  $\mu$ g) + Placebo, will be

compared with those in the participants receiving Fluarix + Spikevax for all 4 influenza strains. Immune responses for SARS-CoV-2, as measured by GM level and SRR at Day 29 by PsVNA in the group of mRNA-1083 (40  $\mu$ g) + Placebo, will be compared with those participants receiving Fluarix + Spikevax for the matched strain.

#### Five Co-primary Endpoints Based on Influenza and SARS-CoV-2 GM level at Day 29

An ANCOVA model will be carried out including the log-transformed HAI or PsVNA levels at Day 29 as the dependent variable, the treatment group as the fixed variable and log transformed baseline HAI or PsVNA levels as a fixed covariate. The model will be adjusted for the stratification factors (influenza vaccine status in the most recent influenza season: received or not received since September 2022).

The GM level will be estimated by the geometric least square mean (GLSM) from the ANCOVA model for each treatment group and corresponding 2-sided 95% CI will be provided. The GLSM and its corresponding CI in log-transformed scale estimated from the ANCOVA model will be back-transformed to the original scale to obtain an estimate of the GM level.

GMR will be estimated by the ratio of GLSM and the corresponding 2-sided 95% and 97.5% CI to assess the immune response difference between the group of mRNA-1083 (40  $\mu$ g) + Placebo and Fluarix + Spikevax and presented by treatment arm (as defined in Section 6.1).

For each strain of influenza and SARS-CoV-2, the NI of GM level will be considered demonstrated between the group of mRNA-1083 (40  $\mu$ g) + Placebo and Fluarix + Spikevax if the lower bound of the 97.5% CI of the GMR is >0.667 based on the prespecified NIM of 1.5.

GM level and GMR at Day 29 will be plotted.

#### Five Co-primary Endpoints Based on Influenza SCR and SARS-CoV-2 SRR at Day 29

Seroconversion and seroresponse are defined as follow:

**Influenza**: Percentage of participants with seroconversion, defined as a Day 29 post-injection level  $\geq$ 1:40 if Baseline is  $\leq$ 1:10 or a 4-fold or greater rise if Baseline is  $\geq$ 1:10 in anti-HA antibodies measured by HAI assay.

**SARS-CoV-2**: Percentage of participants with seroresponse, defined as a Day 29 post-injection level  $\geq$ 4-fold rise if Baseline is  $\geq$  LLOQ or  $\geq$ 4×LLOQ if Baseline value is  $\leq$ LLOQ in the nAb values measured by PsVNA.

The number and percentage of participants with either seroconversion (for influenza) or seroresponse (for SARS-CoV-2) postvaccination at Day 29 will be provided along with the two-sided 95% CI SCR or SRR estimated using the Clopper-Pearson method and presented by treatment arm (as defined in Section 6.1). The difference in either SCR or SRR between the group of mRNA-1083 (40  $\mu$ g) + Placebo and Fluarix + Spikevax, along with its 95% and 97.5% CI estimated using the Miettinen-Nurminen's method will be provided to assess the immune response difference.

For each strain of influenza and SARS-CoV-2, the NI of SCR or SRR will be considered demonstrated between the group of mRNA-1083 (40 µg) + Placebo and Fluarix + Spikevax if the

lower bound of the 97.5% CI of the SCR or SRR difference is >-10% based on the prespecified NIM of 10%.

# 6.3.1.4 Cohort B Substudy (≥50 to <65 Years): Sensitivity, Supplementary and Subgroup Analyses

To assess the consistency of immunogenicity response of mRNA-1083, a sensitivity and subgroup analysis of the co-primary endpoints will be conducted based on PP Immunogenicity Set. A supplementary analysis may be conducted on the Immunogenicity Set if the number of participants in the PPIS and the Immunogenicity Set differs (defined as the difference divided by the total number of participants in the PPIS) by more than 10%. The same statistical methods as for primary analysis will be used for the sensitivity, supplementary and subgroup analyses.

The primary immunogenicity endpoints may be analyzed by subgroup categories available in Table 4. Adjustment will be done for the stratification factor (influenza vaccine status) or baseline antibody level when applicable and the 95% CIs will be calculated. If the number of participants in a subgroup category is less than 10% of sample size in the analysis set, it may be combined with other category for the subgroup analyses.

# 6.3.2 Secondary and Exploratory Immunogenicity Endpoints Analysis

Refer to section 6.3 of this SAP for the definition of the GM level (GMT). The GMFR measures the changes in immunogenicity titers or levels within participants. The GMFR will be calculated using the following formula:

$$2^{\left\{\frac{\sum_{i=1}^{n} \log_{2} \binom{v_{ij}}{v_{ik}}}{n}\right\}} = 2^{\left\{\frac{\sum_{i=1}^{n} \log_{2} (v_{ij}) - \log_{2} (v_{ik})}{n}\right\}}$$

where, for *n* participants,  $V_{ij}$  and  $V_{ik}$  are observed immunogenicity titers or levels for participant *i* at time points *j* and  $k, j \neq k$ .

The 95% CIs for GM level and GMFR will be calculated based on the t distribution of the log-transformed values then back transformed to the original scale for presentation, unless otherwise specified.

Secondary and exploratory immunogenicity endpoints may be conducted for the subgroup categories available in Table 4 of section 6.1.

Additional descriptions will be provided by treatment arm (available in Section 6.1) for the following influenza and SARS-CoV-2 endpoints:

Percentages of participants with seroconversion (influenza) and seroresponse (SARS-CoV-2) with the corresponding 2-sided 95% CI at each post-Baseline time point,

For SARS-CoV-2 antibody value fold rise: Percentage of participants with >= 2-fold rise and =>4-fold rise increases from Baseline values with the corresponding 2-sided 95% CI at each post-Baseline time point,

Percentage of participants with seroresponse (SARS-CoV-2) among participants with values above (>=) LLOQ and below (<) LLOQ values at baseline,

Percentage of participants with values below (<) LLOQ and above (>=) ULOQ values at baseline.

## 6.3.2.1 Cohort A Substudy (≥65 Years)

For the secondary and exploratory endpoints, GM level of HAI, MN or PsVNA with corresponding 95% CI will be provided at each timepoint. GMFR of HAI, MN or PsVNA with corresponding 95% CI at each post-Baseline timepoint over preinjection Baseline at Day 1 will be provided. For the influenza MN descriptive secondary endpoint GMT, an ANCOVA model will be carried out including the log-transformed MN levels at Day 29 as the dependent variable, the treatment group as the fixed variable and log transformed baseline MN levels as a fixed covariate. The model will be adjusted for the stratification factors (age group: 65 to <75 years of age and influenza vaccine status in the most recent influenza season: received or not received since September 2022). A subset of PPIS may be used for exploratory endpoints, including but not limited to immunogenicity analysis at Day 181. Descriptive summary statistics including median, Q1, Q3, minimum, and maximum will also be provided by treatment arm (available in Section 6.1). GM level and GMFR will be plotted at all evaluable timepoints.

#### **6.3.2.2** Cohort B Substudy (≥50 to <65 Years)

For secondary and exploratory endpoints, GM level of HAI, MN or PsVNA with corresponding 95% CI will be provided at each timepoint. GMFR of HAI, MN or PsVNA levels with corresponding 95% CI at each post-Baseline timepoint over preinjection Baseline at Day 1 will be provided. For the influenza MN descriptive secondary endpoint GMT, an ANCOVA model will be carried out including the log-transformed MN levels at Day 29 as the dependent variable, the treatment group as the fixed variable and log transformed baseline MN levels as a fixed covariate. The model will be adjusted for the stratification factors (influenza vaccine status in the most recent influenza season: received or not received since September 2022). A subset of PPIS may be used for exploratory endpoints, including but not limited to immunogenicity analysis at Day 181. Descriptive summary statistics including median, Q1, Q3, minimum, and maximum will also be provided by treatment arm (available in Section 6.1). GM level and GMFR will be plotted at all evaluable timepoints.

#### 6.3.2.3 Immunogenicity Analysis Across Cohort

An additional immunogenicity analysis will be performed for all participants randomized in the mRNA 1083 40  $\mu$ g + Placebo treatment arm in cohorts A and B, in order to evaluate the immunogenicity response between the participants receiving mRNA-1083 included within cohort A substudy ( $\geq$ 65 Years) and participants receiving mRNA-1083 included within cohort B substudy ( $\geq$ 50 to <65 Years). Immune responses for influenza, as measured by GM level and SCR at Day 29 and Day 181 by HAI assay, and at Day 29 for MN assay, in the age group  $\geq$ 65 years, will be compared with the participants in the age group  $\geq$ 50 to <65 years for all 4 influenza strains. Immune responses for SARS-CoV-2, as measured by GM level and SRR at Day 29 and Day 181 by PsVNA in the in the age group  $\geq$ 65 years, will be compared with the participants in the age group  $\geq$ 50 to <65 years for the matched strain. Analysis will be conducted based on PP Immunogenicity Set.

An ANCOVA model will be carried out including the log-transformed HAI, MN or PsVNA levels at Day 29 or Day 181, as applicable, as the dependent variable, and the cohort as the fixed

variable and log transformed baseline HAI, MN or PsVNA levels as a fixed covariate for the GM level assessment. The model may be adjusted for the stratification factors (influenza vaccine status in the most recent influenza season: received or not received since September 2022) when applicable. The GM level will be estimated by the GLSM from the ANCOVA model for each age group and corresponding 2-sided 95% CI will be provided. GMR will be estimated by the ratio of GLSM and the corresponding 2-sided 95% CI to assess the immune response difference between the age group ≥65 years and ≥50 to <65 years and presented by age group.

The number and percentage of participants with either seroconversion (for influenza) or seroresponse (for SARS-CoV-2) postvaccination at Day 29 will be provided along with the two-sided 95% CI of SCR or SRR estimated using the Clopper-Pearson method and presented by age group. The difference in either SCR or SRR between the age group  $\geq$ 65 years and  $\geq$ 50 to <65 years, along with its 95% CI estimated using the Miettinen-Nurminen's method will be provided to assess the immune response difference.

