5.4. Lifestyle Restrictions

Participants must not eat or drink anything hot or cold within 10 minutes before oral temperature is taken.

Participants in the clinical study should defer vaccination with licensed seasonal influenza vaccine or an authorized/licensed COVID-19 vaccine until after completion of their Day 29 visit, and ideally until Day 181. If such vaccines are available, participants should discuss with the Investigators prior to receiving these nonstudy vaccines.

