6.10.2. Concomitant Medications and Therapies

At study site, study staff must record the following information in the eCRF after questioning participants regarding any prohibited or allowed medications taken or nonstudy vaccinations received:

- All nonstudy vaccinations administered within the period starting 28 days before the study injection and through Day 181 or EoS.
- All concomitant medications taken through 28 days after study injection. Antipyretics and analgesics taken prophylactically (ie, taken in the absence of any symptoms in anticipation of an injection reaction) will be recorded as such.
- Systemic steroids (≥10 mg/day of prednisone or equivalent), immunosuppressants, immunoglobulins, or long-acting biological therapies that affect immune responses (eg, infliximab), or blood products administered at any time during the clinical study period after study injection through Day 181 or EoS.
- Any concomitant medications used to prevent or treat either COVID-19 or influenza through EoS.
- Antiviral and antiretroviral medications through Day 181 or EoS.
- Any concomitant medications relevant to or for the treatment of an MAAE from Day 1 through Day 181 or EoS.
- Any concomitant medications relevant to or for the treatment of an SAE or AESI from Day 1 through Day 181 or EoS.
- Any antipyretic or analgesic medications taken to treat or prevent fever or pain, as indicated in the participant's eDiary.

Concomitant medications (including vaccinations) will be coded using the WHO Drug Global.

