6.10.3. Prohibited Therapy

The use of the following concomitant medications and/or vaccines will not require withdrawal of the participant from the clinical study but may determine a participant's evaluability in the PPIS analysis (analysis sets are described in Section 9.4):

- Any investigational or nonregistered product (drug or vaccine) other than the study injections used during the clinical study period.
- Immunosuppressants administered chronically (more than 14 days in total) during the clinical study period. For corticosteroids, ≥10 mg/day of prednisone or equivalent is

mRNA-1083

not permitted. Intra-articular and epidural steroids are not allowed within 28 days before and/or after study injection. Inhaled, nasal, and topical steroids are allowed.

- An authorized or licensed vaccine administered during the period from 28 days before through 28 days after vaccination.
- Immunoglobulins or long-acting biological therapies that affect immune responses (eg, infliximab) or any blood products administered during the clinical study period.
- Antiviral and antiretroviral medications during the clinical study.

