## 5.4 Per Protocol Immunogenicity Set

The Per Protocol Immunogenicity Set (PPIS) will be used as the primary analysis set for analyses of immunogenicity in Cohort A or Cohort B unless otherwise specified. Participants will be analyzed according to the treatment arm to which they were randomized.

The PPIS consists of all the participants in the FAS who comply with the timing of immunogenicity blood sample collections to have both Baseline (see Section 6.1) and Day 29 assessments using a window of -7 to +14 days, have no major dosing error, have negative RT-PCR test for influenza and SARS-CoV-2 on Day 1, and have no major protocol deviations or conditions/medications that affect the immune response.

The major dosing error ranges, available in Table 2, will be used to determine participant exclusion from the PPIS analysis populations.

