#### Step 1:

If the immunogenicity assessments are collected at a scheduled visit, the collected data will be mapped to the nominal scheduled visit, the data collected at scheduled visit will be used.

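### Day 181 HAI and PsVNA results may include titres drawn after a permitted non-study influenza or COVID-19 vaccine, and the plan has no stated rule for them

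*SAP*

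**What the plan says.** **Later vaccination.** Protocol 5.4 asks participants to put off licensed influenza and COVID-19 vaccines "until after completion of their Day 29 visit, and ideally until Day 181" and to talk to the investigator first. Protocol 6.10.2 requires sites to record "All nonstudy vaccinations administered within the period starting 28 days before the study injection and through Day 181 or EoS".

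**Analysis set.** Among the items in Protocol 6.10.3 that may decide PPIS evaluability, the one on licensed vaccines reads "An authorized or licensed vaccine administered during the period from 28 days before through 28 days after vaccination". SAP 5.4 sets the timing condition as "both Baseline (see Section 6.1) and Day 29 assessments using a window of -7 to +14 days". The same paragraph excludes participants for conditions or medications bearing on immune response. It gives no time limit and does not mention vaccines or Day 181.

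**Visit mapping.** SAP Appendix C, Step 1: "If the immunogenicity assessments are collected at a scheduled visit, the collected data will be mapped to the nominal scheduled visit".

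**Day 181 outputs.**
- SAP 6.3.2 gives "Percentages of participants with seroconversion (influenza) and seroresponse (SARS-CoV-2) with the corresponding 2-sided 95% CI at each post-Baseline time point".
- SAP 6.3.2.1 and 6.3.2.2 give GM level and GMFR at each timepoint, and allow a PPIS subset to be used for Day 181.
- SAP 6.3.2.3 covers "Immune responses for influenza, as measured by GM level and SCR at Day 29 and Day 181 by HAI assay" and SARS-CoV-2 by PsVNA at the same days. Its ANCOVA has cohort, log baseline and possibly influenza vaccine stratum, with no term for later vaccination. On the population it says "Analysis will be conducted based on PP Immunogenicity Set".

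**Reporting of later vaccines.** SAP 6.2.4 tabulates influenza or COVID-19 vaccination only up to 28 days after injection. All non-study vaccinations also go into a participant listing.

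**The concern.** A Day 181 titre is naturally read as what remains of the response to the Day 1 injection. If a participant had a further influenza vaccine in between, the HAI result also reflects that vaccine; likewise PsVNA after a further COVID-19 vaccine. Followed as written, the plan pools such titres with the rest, and no summary table shows how many there are.

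At stake is the reading of Day 181 results as persistence: GM level, GMFR, SCR and SRR by arm, and the age-cohort comparison, which is one analysis yielding five Day 181 GMRs (four HAI strains and one PsVNA strain).

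**Working it through.** **Step 1. Is there a rule?** Following one scheduled Day 181 sample, drawn after a non-study vaccine given after Day 29:
- the vaccine is permitted (Protocol 5.4) and its date is recorded (Protocol 6.10.2);
- it falls outside the 28-day limit of the licensed-vaccine item (Protocol 6.10.3);
- the participant still meets PPIS timing, which looks only at Baseline and Day 29 (SAP 5.4);
- the sample is mapped to Day 181 by nominal visit (SAP Appendix C);
- it enters the Day 181 results (SAP 6.3.2 to 6.3.2.3).

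No step excludes, flags or adjusts for it.

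**Step 2. Inputs.** The documents state no uptake rate, no boost size and no Day 181 precision, so there is no plan figure to reproduce. From the documents:
- SD of the natural-log level 1.5 (Protocol 9.3.1; a Day 29 planning value, assumed here for Day 181);
- the first 800 participants per cohort at Day 181 (SAP 6.3), so about 400 per arm at 1:1;
- planning rates in the comparator arm of 70% for influenza A and SARS-CoV-2 and 60% for influenza B (Protocol 9.3.1).

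Uptake p, residual fold-boost f, and the rate without later vaccination are assumptions.

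**Step 3. GM level within an arm.** If a fraction p has titres multiplied by f, the geometric mean is multiplied by f^p.

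| Uptake | Boost | Inflation |
|---|---|---|
| 2% | 1.5-fold | 1.5^0.02 = 1.008 |
| 2% | 2-fold | 2^0.02 = 1.014 |
| 10% | 2-fold | 2^0.10 = 1.072 |
| 10% | 4-fold | 4^0.10 = 1.149 |
| 20% | 4-fold | 4^0.20 = 1.320 |

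GMFR is inflated by the same factor, because the baseline is unchanged.

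**Step 4. SCR and SRR.** Inflation = p × (rate if revaccinated − rate if not). At p = 10%, with an assumed 20% to 50% rate otherwise:
- using 70% (A strains, SARS-CoV-2): 0.10 × (70 − 50) = 2 points to 0.10 × (70 − 20) = 5 points;
- using 60% (B strains): 0.10 × (60 − 50) = 1 point to 0.10 × (60 − 20) = 4 points.

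**Step 5. Age-cohort GMR.** The factor is fA^pA / fB^pB.
- Equal uptake and equal boost: 1.00.
- Uptake differing by 10 points, both boosts 4-fold: 4^0.10 = 1.15, or 0.87 in the other direction.
- Uptake 20% in both, boosts 4-fold and 3-fold: (4/3)^0.20 = 1.06, or 0.94.

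For scale, the SE of the log GMR without baseline adjustment is 1.5 × √(2/400) = 0.106, so the 95% CI factor is exp(1.96 × 0.106) = 1.23. With 15% drop-out (340 per group) it is 1.25.

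**The case against.** Five points can be made for the plan.

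1. *Uptake may be close to nil.* Every participant gets influenza and COVID-19 antigens on Day 1 and is asked to defer more. This stands. A reader might infer that the Day 181 data do contain boosted titres; the documents show only that they may.

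2. *The general PPIS exclusion could cover later vaccines.* Protocol 6.10.2 counts vaccinations among concomitant medications, so the wording allows it. But it states no Day 181 rule, and the specific vaccine item stops at 28 days. PPIS-excluding deviations are fixed before database lock and unblinding (SAP 6.2.5), while the primary analysis follows completion of Day 29 (SAP 6.7.1), so later doses need not be known then.

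3. *Late vaccinees could be left out of the Day 181 subset.* Within cohorts this is true, and it would not touch Day 29 data. It is room for a rule, not a rule. The age-cohort analysis names the full PPIS, so removing people through the PPIS clause there would also drop valid Day 29 titres.

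4. *Late doses are listed.* They are, per participant. The summary table still ends at 28 days.

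5. *Reporting observed titres regardless of later vaccination is legitimate.* It is, and it should be kept. The gap is that the reader cannot tell how far those results can be read as persistence.

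A reader might also infer that the age-cohort GMR is biased. That needs unequal uptake or boost. The only reason the documents suggest concerns influenza: Protocol 2.2 notes a US preference for a high-dose product at 65 and over. The COVID-19 comparator is the same in both cohorts (Protocol 1.1), so nothing comparable is offered for PsVNA.

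**Conclusion.** The missing rule is clear from the text; the size of its effect is unknown. With any uptake and a positive residual boost, within-arm Day 181 GM level, GMFR, SCR and SRR can overstate the lasting response to the study vaccine: negligibly at low uptake (about 1.01 at 2%), noticeably at higher uptake (1.15 to 1.32 at 10% to 20% with a 4-fold boost). The age-cohort GMRs move only if uptake or boost differs by cohort, in either direction; the illustrated shifts of 1.06 and 1.15 lie within the CI factor of 1.23.

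The reach is limited. No Day 181 GMR between treatment arms is planned. MN is compared at Day 29 only. SAP 6.3.2.3 names Day 181 SCR and SRR, but its method paragraph describes rates at Day 29 only. The within-cohort Day 181 endpoints are optional (SAP 3.3), and endpoints outside the testing sequence are descriptive (SAP 6.4). A reader might infer a threat to the main conclusions; the documents do not support that, because the co-primary and superiority tests use Day 29. This is a cheap improvement, not a flaw in the confirmatory analysis.

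**What to change.** In SAP 6.3.2 and 6.3.2.3, state that Day 181 HAI and PsVNA results are shown side by side in two versions:
1. all samples, whatever vaccine came later;
2. as a sensitivity analysis, setting aside HAI results drawn after a recorded non-study influenza vaccine, and PsVNA results drawn after a recorded non-study COVID-19 vaccine.

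Label version 2 *participants without recorded later vaccination against that pathogen*, and say that it is not read as the level that would be seen without later vaccination. Leave Day 29 PPIS membership unchanged.

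In SAP 6.2.4, extend the influenza and COVID-19 vaccine summary to Day 181, by arm and cohort.

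**Cost.** SAP wording, one pathogen-specific flag from dates already collected, and one longer summary line. Version 2 is slightly less precise. From 400 per group, setting aside 10% leaves 360 and a CI factor of exp(1.96 × 1.5 × √(2/360)) = 1.25; setting aside 30% leaves 280 and 1.28. From 340 per group the factors are 1.27 and 1.31. People who take no later vaccine may differ from those who do, and titres raised by infection after Day 29 remain in both versions. Hence both are shown and neither replaces the other.
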